6.6.2 Secondary Efficacy Endpoints

The secondary efficacy endpoints include ORR, EFS, LFS, PFS, OS, the rate of transfusion independence, and the duration of transfusion independence (see Section 2.3.2), which will be analyzed as follows:

- ORR will be assessed as the proportion of patients who obtain a CR, CRp, CRI, CRh or PR (as defined by the IWG 2003 and ELN 2010) after up to six cycles of combination therapy. The proportions will be calculated for categorical variables by dividing the number of patients with a positive response by the number of patients. Patients with no response assessments (for whatever reason) will be considered non-responders.
- For EFS, data from patients not known to have any of the listed events will be censored on the date they were last examined. For patients who do not achieve a CR, CRp, CRh, or CRI, EFS is defined as the point of progression or death, whichever comes first.
- For LFS, data from patients not known to have any of these events will be censored on the date they were last examined.
- For OS, data for patients who did not die will be censored at the date of last study visit or the last known date to be alive, whichever is later. If no postbaseline data are available, OS will be censored at the date of first treatment plus 1 day.
- Rate of transfusion independence is defined as the proportion of patients who achieve transfusion independence at any time during study treatment. Transfusion independence is defined as achieving any continuous 56-day window without requiring platelet or RBC transfusions.
- Duration of transfusion independence is defined as the number of consecutive days of transfusion independence, measured from 1 day after last transfusion to disease progression or subsequent transfusion.

6.7 IMMUNOGENICITY ANALYSES

The immunogenicity analysis population will consist of all patients with at least one ADA assessment. Patients will be grouped according to treatment received or, if no treatment is received prior to study discontinuation, according to treatment assigned.

The number and proportion of ADA-positive patients and ADA-negative patients at baseline (baseline prevalence) and after drug administration (postbaseline incidence) will be summarized by treatment group. When determining postbaseline incidence, patients are considered to be ADA positive if they are ADA negative or have missing data at baseline but develop an ADA response following study drug exposure (treatment-induced ADA response), or if they are ADA positive at baseline and the titer of one or more postbaseline samples is at least 0.60-titer unit greater than the titer of the baseline sample (treatment-enhanced ADA response). Patients are considered to be ADA negative if they are ADA negative or have missing data at baseline and all postbaseline samples are negative, or if they are ADA positive at baseline but do not

have any postbaseline samples with a titer that is at least 0.60-titer unit greater than the titer of the baseline sample (treatment unaffected).

The relationship between ADA status and safety, efficacy, PK, and biomarker endpoints will be analyzed and reported via descriptive statistics.

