3.1.1 Overview of Study Design

[Figure 1](#) presents an overview of the study design. A schedule of activities is provided in [Appendix 1](#).

Figure 1 Study Schema

Atezo=atezolizumab; DLT=dose-limiting toxicity; Q2W=every 2 weeks; QW=once a week.

Note: On days when both atezolizumab and Hu5F9-G4 are administered (Day 22 of Cycle 1 and Days 8 and 22 of subsequent cycles), Hu5F9-G4 should be administered first and *the interval between Hu5F9-G4 and atezolizumab infusions should follow guidelines as outlined in [Table 2](#).*

The proposed treatment regimen during Cycle 1 is a biomarker-driven treatment plan designed to assess the effect of single-agent Hu5F9-G4 on markers of immune activation in AML. This safety cohort is designed to assess the safety, tolerability, and clinical activity of Hu5F9-G4 in combination with atezolizumab based on the following schedule:

- Atezolizumab: Atezolizumab will be administered to patients by IV infusion at a fixed dose of 840 mg, starting on Day 22 of Cycle 1. In subsequent cycles (Cycles 2 and beyond), 840 mg of IV atezolizumab will be given every 2 weeks (Q2W) on Days 8 and 22 of each 28-day cycle.
- Hu5F9-G4: Two priming doses of 1 mg/kg of Hu5F9-G4 will be administered to patients by continuous IV infusion on Days 1 and 4 of Cycle 1, followed by loading doses of 15 mg/kg IV on Day 8 and 30 mg/kg IV on Day 11. Starting on Day 15 of Cycle 1, Hu5F9-G4 maintenance will be given by IV infusion at a dose of 30 mg/kg once a week (QW) of each 28-day cycle. On days when both atezolizumab and Hu5F9-G4 are administered (Day 22 of Cycle 1 and Days 8 and 22 of subsequent cycles), Hu5F9-G4 should be administered first and *the interval between Hu5F9-G4 and atezolizumab infusions should follow guidelines as outlined in Table 2*.

If DLTs are observed in $\geq 33\%$ of patients (i.e., 2 or more of 6 patients) in this initial safety cohort, a dose de-escalation cohort of 6 patients will be enrolled. The dosing schedules for this de-escalation cohort will be as follows:

- Atezolizumab will be administered to patients by IV infusion at a fixed dose of 840 mg, starting on Day 22 of Cycle 1. In subsequent cycles, 840 mg of atezolizumab administered by IV infusion will be given Q2W on Days 8 and 22 of each 28-day cycle.

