- Hu5F9-G4 will be given as two priming doses of 1 mg/kg IV on Days 1 and 4, followed by loading doses of 10 mg/kg IV on Day 8 and 15 mg/kg on Day 11. Starting on Day 15, maintenance treatment with Hu5F9-G4 will be given by IV infusion at a dose of 15 mg/kg QW.
- If $<33\%$ (i.e., 1 or fewer of 6 patients) *patients in the de-escalation cohort experience a DLT*, an expansion cohort of 9 patients will be enrolled to further test the safety and anti-tumor activity of atezolizumab in combination with Hu5F9-G4, using the same dosing regimen

If DLTs are observed in $<33\%$ of patients (i.e., 1 or fewer of 6 patients) in the initial safety cohort, an expansion cohort of 15 patients will be enrolled to further test the safety and anti-tumor activity of atezolizumab in combination with Hu5F9-G4, using the same dosing regimen.

Study treatment will be administered until unacceptable toxicity or loss of clinical benefit, as determined by the investigator, after local biopsy results (if available) and clinical status (e.g., symptomatic deterioration such as pain secondary to disease) are assessed.

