4.5.10 Anti-Drug Antibody Testing

Atezolizumab may elicit an immune response. Patients with signs of any potential immune response to atezolizumab will be closely monitored. Validated screening, confirmatory, and titer assays will be employed to detect ADAs at multiple timepoints before, during, and after treatment with atezolizumab and Hu5F9-G4 (see [Appendix 2](#) for the schedule of ADA assessments). ADA response will be correlated with relevant clinical endpoints to understand its clinical significance. Additional ADA assays (e.g., neutralizing antibody assay) may be employed to further characterize ADA response.

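### Ever/never ADA status in Section 6.7 depends on time on treatment, so relating it to efficacy and safety can produce a false association when ADA has no effect

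*Combined protocol and SAP*

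**What the plan says.** Section 6.7 sets the rule. A patient who is negative or missing at baseline becomes positive on any induced response after dosing. A patient positive at baseline becomes positive if the "titer of one or more postbaseline samples is at least 0.60-titer unit greater than the titer of the baseline sample". Negative patients are those who are "ADA negative or have missing data at baseline and all postbaseline samples are negative", plus baseline-positive patients without that titer rise. The rule gives no cut-off date, minimum exposure or minimum number of postbaseline samples.

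The population is broad: "The immunogenicity analysis population will consist of all patients with at least one ADA assessment". One baseline sample is enough to enter it.

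The same section then says "The relationship between ADA status and safety, efficacy, PK, and biomarker endpoints will be analyzed and reported via descriptive statistics", and Section 4.5.10 gives the purpose: "ADA response will be correlated with relevant clinical endpoints to understand its clinical significance". Neither section mentions a landmark, a time-dependent status or an adjustment for exposure.

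Section 3.1.1 makes the duration of treatment depend on outcome: "Study treatment will be administered until unacceptable toxicity or loss of clinical benefit, as determined by the investigator". Appendix 2 schedules on-treatment ADA samples up to Cycle 16 for atezolizumab and Cycle 15 for Hu5F9-G4. It adds a discontinuation sample for both drugs and a sample 120 ± 30 days after the last atezolizumab dose for atezolizumab only.

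**The concern.** Positive status can only be earned by remaining under observation long enough for an antibody to arise and be sampled. A patient who progresses or dies early has little exposure and few samples, and tends to stay negative. A patient with only a baseline sample would fall into the negative group by default. A patient in remission goes on being dosed and sampled. The grouping therefore uses information collected after the outcome clock has started, and the number of chances to turn positive is itself a consequence of outcome.

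Safety is affected in the same way. Section 5.3.1 collects adverse events until 30 days after the final dose, so event counts also grow with time on treatment.

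What is at stake is the interpretation promised in Section 4.5.10. The distortion makes positive patients look better on efficacy, so a real loss of efficacy from ADA could be hidden or reversed.

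**Working it through.** The documents give no figure for this analysis, so there is none to reproduce. The check asks what the stated rule yields when ADA has no effect at all.

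**Step 1: sampling days.** Study day = 28 × (cycle − 1) + day in cycle. Atezolizumab begins "starting on Day 22 of Cycle 1" (Section 3.1.1), and its baseline ADA sample is taken that day. Postbaseline atezolizumab samples in Appendix 2 are:

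- C2D8, C2D22, C3D22 and C4D22: Days 36, 50, 78 and 106.
- C8D22, C12D22 and C16D22: Days 218, 330 and 442, only while treatment continues.
- Discontinuation, and 120 days after the last atezolizumab dose.

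**Step 2: chance of being classed positive.** Assume, for illustration, a constant onset hazard that gives 40% by 6 months (182 days) of exposure, unrelated to outcome and continuing after the last dose. Then λ = −ln(0.6)/182 = 0.5108/182 = 0.002807 per day, and P(positive by day s) = 1 − exp(−λ(s − 22)).

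| Patient | Last sample | s − 22 | P(positive) |
|---|---|---|---|
| Early failure, no later sample | Day 50 | 28 | 7.6% |
| Last dose Day 50, survives to the 120-day sample | Day 170 | 148 | 34.0% |
| Still treated at C8D22 | Day 218 | 196 | 42.3% |
| Last dose Day 218, survives to the 120-day sample | Day 338 | 316 | 58.8% |

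The 120-day sample narrows the difference but does not close it, and only survivors provide it. Hu5F9-G4 has no such sample.

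**Step 3: full simulation, no ADA effect, all planned samples.** The documents do not give the following, so they are assumed: median treatment of 2, 3 or 6 months (exponential), median survival of 3 months after progression, and four onset patterns (constant hazard at two levels, and two in which 30% convert). Follow-up is cut at 15 months. HR is the ratio of event rates, ADA-positive to ADA-negative.

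| Onset pattern | PFS HR | OS HR |
|---|---|---|
| Constant hazard, 20% or 40% by 6 months | 0.39–0.65 | 0.39–0.64 |
| 30% convert, mean onset 6 weeks | 0.87–0.90 | 0.85–0.88 |
| 30% convert, all by first postbaseline sample | 0.98–0.99 | 0.98–0.99 |

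Under constant hazard, 9–20% of patients treated for 78 days or less are positive, against 30–68% of those treated for more than 6 months. With a 3-month median and 40% by 6 months, median PFS is 5.7 months in positive and 2.9 months in negative patients.

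Assume further about 15% responders who stay longer, and an adverse event rate of 0.10 per month. Constant hazard then gives response in 29–33% of positive against 13–15% of negative patients, and any such adverse event in 43–46% against 27–30%. With onset by the first sample the figures are 19% against 18%, and 33% against 32%.

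**Step 4: range in months.** A second model assumes remission in 10–25%, median time to progression of 1.5–2.5 months in non-responders, 30–50% prone to ADA, and median onset of 1.5–3 months after first atezolizumab. Responder duration and survival after progression also had to be assumed. With all planned samples the false gap in median PFS is about 0.7–2.3 months; omitting the 120-day sample raises it to 1.2–3.1. With very early onset it is about 0.1 month.

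**Step 5: the remedy.** Patients event-free and still treated on Day 50 have all been scheduled for the same samples (Days 36 and 50), so status at that date reflects onset time alone. In the second model a Day 50 landmark in event-free patients brings both the PFS and OS gaps to within about 0.1 month. In the first model, a Day 78 landmark gives PFS HR 0.98–1.03 and time-dependent status gives 0.98–1.02.

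OS is less tidy if time on and off treatment is ignored. Across runs with and without the off-treatment samples, a landmark on patients merely alive at Day 78 leaves OS HR 0.86–1.01, and time-dependent status gives 0.85–1.37.

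With a 3-month median (91.3 days), 21 × 2^(−50/91.3) ≈ 14 patients would remain on treatment at Day 50 and 21 × 2^(−78/91.3) ≈ 12 at Day 78.

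**The case against.** Several points on the other side have weight.

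- *The link is inferred.* The ever/never rule is introduced for postbaseline incidence, and the later sentence says only ADA status. This is fair. But no other postbaseline status is defined, so an analyst following the section would use this one.
- *Off-treatment samples protect the comparison.* They reduce the distortion, as Steps 2 and 4 show, but do not remove it.
- *Onset time decides the size.* This stands in full. If nearly all ADA arises by the first postbaseline sample, there is almost no distortion. At 21 patients and a 3-month median, the unadjusted PFS HR falls below 1 in 92% of simulated trials under constant hazard at 40%, in 57% with 6-week onset, and in 47% with early onset.
- *The analysis is descriptive.* Section 6.1 disclaims power and type I error considerations, and no decision rests on the table. That limits the consequence, but a descriptive table can still be systematically misleading.
- *The landmark has a price.* It cannot assess ADA that arises later, and it shrinks an already small group.

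A reader might go further and infer that positive patients are bound to look better, that the plan carries an inflated false-positive rate, or that groups formed from on-treatment biomarkers share the flaw. The documents support none of these. They give no onset time and plan no test by ADA status. Section 6.8 has no ever/never rule, and its biomarker relationships are optional.

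**Conclusion.** The concern holds in conditional form. Following Section 6.7 as written can create a false association between ADA positivity and longer PFS or OS, more responses and more adverse events. Under an assumed median onset of 1.5–3 months and all planned samples, the false median PFS gap is about 0.7–2.3 months. It is larger if onset is spread evenly over treatment and negligible if onset is almost entirely early. These sizes rest on assumed onset, response and progression times that the documents do not supply.

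The consequence is a misleading reading of clinical significance in a descriptive comparison of at most 21 patients. ADA incidence, DLT decisions, the CR rate and DOR are unaffected. The change is worth making because it is cheap and because the likely direction of error would make ADA look harmless.

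**What to change.** Amend Section 6.7 as follows.

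- Keep the ever/never classification for the incidence table only.
- For efficacy by ADA status, classify patients at a fixed landmark sample: for example C2D22 (Day 50) for atezolizumab, with a corresponding early sample for Hu5F9-G4. Include only patients with a postbaseline sample who are alive and event-free at the landmark, and count outcomes from that date.
- Alternatively, treat ADA status as time-dependent for PFS. If OS is shown by time-dependent status, state that time on and off treatment can still distort it.
- Report adverse events by ADA status per patient-month.

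The cost is one paragraph, using samples already in Appendix 2. Patients with an event before the landmark leave this one comparison, and ADA arising after it counts as negative; the text should say so.

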6.8 BIOMARKER ANALYSES

The exploratory data generated with the use of fresh cancer tissues and/or blood samples (see Section 4.5.7.2) may be listed by patient, dose, cohort, and response status. In addition, the relationships between these data and observed safety or clinical activity may be assessed.

7. DATA COLLECTION AND MANAGEMENT

7.1 DATA QUALITY ASSURANCE

The Sponsor will be responsible for data management of this study, including quality checking of the data. Data entered manually will be collected via EDC through use of eCRFs. Sites will be responsible for data entry into the EDC system. In the event of discrepant data, the Sponsor will request data clarification from the sites, which the sites will resolve electronically in the EDC system.

The Sponsor will produce an EDC Study Specification document that describes the quality checking to be performed on the data. Other electronic data will be sent directly to the Sponsor, using the Sponsor's standard procedures to handle and process the electronic transfer of these data.

eCRFs and correction documentation will be maintained in the EDC system's audit trail. System backups for data stored by the Sponsor and records retention for the study data will be consistent with the Sponsor's standard procedures.

7.2 ELECTRONIC CASE REPORT FORMS

eCRFs are to be completed through use of a Sponsor-designated EDC system. Sites will receive training and have access to a manual for appropriate eCRF completion. eCRFs will be submitted electronically to the Sponsor and should be handled in accordance with instructions from the Sponsor.

All eCRFs should be completed by designated, trained site staff. eCRFs should be reviewed and electronically signed and dated by the investigator or a designee.

At the end of the study, the investigator will receive patient data for his or her site in a readable format that must be kept with the study records. Acknowledgement of receipt of the data is required.

7.3 SOURCE DATA DOCUMENTATION

Study monitors will perform ongoing source data verification and review to confirm that critical protocol data (i.e., source data) entered into the eCRFs by authorized site personnel are accurate, complete, and verifiable from source documents.

Source documents (paper or electronic) are those in which patient data are recorded and documented for the first time. They include, but are not limited to, hospital records, clinical and office charts, laboratory notes, memoranda, evaluation checklists, pharmacy dispensing records, recorded data from automated instruments, copies of transcriptions that are certified after verification as being accurate and complete, microfiche, photographic negatives, microfilm or magnetic media, X-rays, patient files, and records kept at pharmacies, laboratories, and medico-technical departments involved in a clinical trial.

Before study initiation, the types of source documents that are to be generated will be clearly defined in the Trial Monitoring Plan. This includes any protocol data to be entered directly into the eCRFs (i.e., no prior written or electronic record of the data) and considered source data.

Source documents that are required to verify the validity and completeness of data entered into the eCRFs must not be obliterated or destroyed and must be retained per the policy for retention of records described in Section [7.5](#).

To facilitate source data verification and review, the investigators and institutions must provide the Sponsor direct access to applicable source documents and reports for trial-related monitoring, Sponsor audits, and IRB review. The study site must also allow inspection by applicable health authorities.

7.4 USE OF COMPUTERIZED SYSTEMS

When clinical observations are entered directly into a study site's computerized medical record system (i.e., in lieu of original hardcopy records), the electronic record can serve as the source document if the system has been validated in accordance with health authority requirements pertaining to computerized systems used in clinical research. An acceptable computerized data collection system allows preservation of the original entry of data. If original data are modified, the system should maintain a viewable audit trail that shows the original data as well as the reason for the change, name of the person making the change, and date of the change.

7.5 RETENTION OF RECORDS

Records and documents pertaining to the conduct of this study and the distribution of IMP, including eCRFs, electronic or paper patient-reported data (if applicable), Informed Consent Forms, laboratory test results, and medication inventory records, must be retained by the Principal Investigator for 15 years after completion or discontinuation of

the study or for the length of time required by relevant national or local health authorities, whichever is longer. After that period of time, the documents may be destroyed, subject to local regulations.

No records may be disposed of without the written approval of the Sponsor. Written notification should be provided to the Sponsor prior to transferring any records to another party or moving them to another location.

Roche will retain study data for 25 years after the clinical study report has been completed or for the length of time required by relevant medical or local health authorities, whichever is longer.

8. ETHICAL CONSIDERATIONS

8.1 COMPLIANCE WITH LAWS AND REGULATIONS

This study will be conducted in full conformance with the ICH E6 guideline for Good Clinical Practice and the principles of the Declaration of Helsinki, or the applicable laws and regulations of the country in which the research is conducted, whichever affords the greater protection to the individual. The study will comply with the requirements of the ICH E2A guideline (Clinical Safety Data Management: Definitions and Standards for Expedited Reporting). Studies conducted in the United States or under a U.S. Investigational New Drug (IND) Application will comply with U.S. FDA regulations and applicable local, state, and federal laws. Studies conducted in the European Union or European Economic Area will comply with the E.U. Clinical Trial Directive (2001/20/EC and General Data Protection Regulation as applicable) and applicable local, regional, and national laws.

8.2 INFORMED CONSENT

The Sponsor's sample Informed Consent Form (and ancillary sample Informed Consent Forms such as a Child's Informed Assent Form or Mobile Nursing Informed Consent Form, if applicable) will be provided to each site. If applicable, it will be provided in a certified translation of the local language. The Sponsor or its designee must review and approve any proposed deviations from the Sponsor's sample Informed Consent Forms or any alternate consent forms proposed by the site (collectively, the "Consent Forms") before IRB submission. The final IRB-approved Consent Forms must be provided to the Sponsor for health authority submission purposes according to local requirements.

If applicable, the Informed Consent Form will contain separate sections for any optional procedures. The investigator or authorized designee will explain to each patient the objectives, methods, and potential risks associated with each optional procedure.

Patients will be told that they are free to refuse to participate and may withdraw their consent at any time for any reason. A separate, specific signature will be required to document a patient's agreement to participate in optional procedures. Patients who decline to participate will not provide a separate signature.

The Consent Forms must be signed and dated by the patient or the patient's legally authorized representative before his or her participation in the study. The case history or clinical records for each patient shall document the informed consent process and that written informed consent was obtained prior to participation in the study.

The Consent Forms should be revised whenever there are changes to study procedures or when new information becomes available that may affect the willingness of the patient to participate. The final revised IRB-approved Consent Forms must be provided to the Sponsor for health authority submission purposes.

Patients must be re-consented to the most current version of the Consent Forms (or to a significant new information/findings addendum in accordance with applicable laws and IRB policy) during their participation in the study. For any updated or revised Consent Forms, the case history or clinical records for each patient shall document the informed consent process and that written informed consent was obtained using the updated/revised Consent Forms for continued participation in the study.

A copy of each signed Consent Form must be provided to the patient or the patient's legally authorized representative. All signed and dated Consent Forms must remain in each patient's study file or in the site file and must be available for verification by study monitors at any time.

For sites in the United States, each Consent Form may also include patient authorization to allow use and disclosure of personal health information in compliance with the U.S. Health Insurance Portability and Accountability Act (HIPAA) of 1996. If the site utilizes a separate Authorization Form for patient authorization for use and disclosure of personal health information under the HIPAA regulations, the review, approval, and other processes outlined above apply except that IRB review and approval may not be required per study site policies.

